CLINICAL STUDY CODE	INTENT study	
EUDRACT NO.	2014-001991-76	
PROTOCOL VERSION	Version 5.0; 201600405	
INDICATION	First episode of steroid-sensitive nephrotic syndrome (SSNS) in children in remission (N04.9)	
	Nephrotic syndrome: MedDRA term 10029164 (version: 16.2, LLT)	
OBJECTIVES	To demonstrate that mycophenolate mofetil as initial treatment is not inferior to standard treatment with prednisone related to relapse rate within 24 months	
	Primary efficacy endpoint:	
	Occurrence of treated relapse within 24 months after end of initial treatment (non-inferiority)	
	Key secondary endpoint(s):	
	 Course of the disease: Time from remission to first relapse; number of relapses; mean relapse rate per patient and year; incidence of frequent relapsers Prednisone-associated toxicity: Cumulative prednisone dose (mg/m² BSA); body mass index (standard deviation score); striae; hypertrichosis; acne; arterial hypertension; disturbances of carbohydrate and lipid metabolism; growth failure; cataract; glaucoma; psychological disturbances MMF-associated toxicity: diarrhea; blood cell count disturbances, infections 	
PHASE	III	
INVESTIGATIONAL MEDICINAL	INN: Mycophenolate mofetil (MMF)	
PRODUCT(S)	ATC-code: L04AA06	
	MMF is administered in liquid form (CellCept suspension®, Roche AG)	
	Mycophenolate mofetil (MMF) 1200 mg/m² body surface area (BSA) per day, until a total initial treatment duration of 12 weeks is reached (induction of remission with prednisone + maintenance of remission with MMF (intervention).	

	MMF is administered in conjunction with alternate day	
	prednisone 40 mg/m ² BSA for the first 2 weeks.	
REFERENCE DRUG	INN: Prednisone	
	ATC-code: H02AB07	
	Prednisone is administered as tablet	
	Continuing the standard protocol for children with first episode of SSNS according to GPN guidelines: 60 mg prednisone/m² BSA per day for 6 weeks followed by alternate day prednisone 40 mg/m² BSA for another 6 weeks	
STUDY DESIGN	Prospective, randomized, multicenter, controlled, open, parallel group study	
STUDY POPULATION	Inclusion Criteria	
	 First episode of steroid-sensitive nephrotic syndrome (SSNS) 	
	 In remission induced by daily glucocorticoids within 28 days 	
	 Male and female children aged ≥ 1 year and ≤ 10 years at beginning of study (typical age range of patients with SSNS) 	
	Ability of the persons having care and custody of the child to understand character and individual consequences of clinical study	
	Written informed consent of the persons having care and custody of the child.	
	Exclusion Criteria	
	Secondary nephrotic syndrome	
	 estimated glomerular filtration rate (eGFR) <90 ml/min x 1.73 m² BSA 	
	 Ongoing treatment with systematically admini- stered glucocorticoids or other immunosuppressive drugs at time of first episode of nephrotic syndrome 	
	 Hemoglobin concentration of ≤9 g/dL 	
	 Leucocyte count of ≤2.500/μl 	
	Severe chronic gastrointestinal disease History of hypersonsitivity to mycephonelate	
	 History of hypersensitivity to mycophenolate mofetil or to any drug with similar chemical structure or to any excipient present in the pharmaceutical form of suspension of mycophenolate mofetil (CellCept suspension®) Refusal of subject (please see also chapter 10.5) Participation in other clinical studies or observation period of competing studies, respectively 	

SAMPLE SIZE	To be assessed for eligibility (n = 400)	
	To be allocated to study (n = 340)	
	To be analyzed (n = 272, according to per protocol)	
STUDY DURATION	Total study duration:	[78 months]
	Duration of clinical phase:	[63 months]
	Beginning of the preparation phase:	[03/2014]
	FSI (first subject in):	[01/2015]
	LSI (last subject in):	[01/2018]
	LSO (last subject out):	[04/2020]
	DBL (database lock):	[07/2020]
	Statistical analyses completed:	[08/2020]
	Study report completed: [04/2021]	
STATISTICAL ANALYSIS	Efficacy/test accuracy:	
	Non-inferiority analysis to compare the relapse rates using the Farrington-Manning test.	
	Description of the primary efficacy/test accuracy analysis and population:	
	Confirmatory analysis will be based on the per-protocol population as well as the intention to treat population.	
	Secondary endpoints:	
	Descriptive p-values of the corresponding statistical tests comparing the treatment groups and associated 95% confidence intervals will be given.	
	Safety:	
	Rates of adverse and serious adverse events will be calculated with 95% confidence intervals for treatment group comparisons.	
NUMBER OF CENTRES	app. 45 centers planned	
FINANCING	BMBF (Bundesministerium für Bildung und Forschung), Förderkennzeichen: 01KG1301	

FLOW CHART/ STUDY SCHEDULE

1. Study flow

alternate day = every second day

INTENT study Page 12 of 64

ABBREVIATIONS

AE Adverse Event

AMG German Drug Law (Deutsches Arzneimittelgesetz)

ATC Anatomical-Therapeutic-Chemical Code, part of WHO-DRL (Drug

Reference List)

BfArM Bundesinstitut für Arzneimittel und Medizinprodukte

(Federal Institute for Drugs and Medical Devices, Germany)

BMI Body mass index
BP Blood pressure
BSA Body surface area
CRF Case Report Form
DBL Data Base Lock

DFG Deutsche Forschungsgemeinschaft
DSMB Data and Safety Monitoring Board

EC Ethics Committee
ECG Electrocardiogram
Echo Echocardiogram

eGFR estimated glomerular filtration rate

FD Financial Disclosure
FPI First Patient In

GCP Good Clinical Practice

GCP-V Good Clinical Practice Ordinance (GCP-Verordnung)

GPN German Society for Pediatric Nephrology

IB Investigator's Brochure

ICH International Conference on Harmonization of Technical Requirements for

Registration of Pharmaceuticals for Human Use

ICH GCP ICH harmonized tripartite guideline on GCP IMBI Institute of Medical Biometry and Informatics

IMP Investigational Medicinal Product

IMPD Investigational Medicinal Product Dossier

INN International Nonproprietary Name

ISF Investigator Site File
ITT Intention-to-Treat

KKS Coordination Center for Clinical Studies (Koordinierungszentrum für

Klinische Studien)

LKP Coordinating Investigator according to AMG (Leiter der klinischen

Prüfung)

LPO Last Patient Out
LSI Last Subject In
LSO Last Subject Out

MedDRA Medical Dictionary for Regulatory Activities

MMF Mycophenolate mofetil
PI Principal Investigator

PP Per-Protocol

Q Quarter (time span)
SAE Serious Adverse Event
SC Steering Committee

SmPC Summary of Product Characteristics SSNS Steroid-sensitive nephrotic syndrome

SUSAR Suspected Unexpected Serious Adverse Reaction TDM MPA therapeutic drug monitoring of mycophenolic acid

TMF Trial Master File

WHO World Health Organization

1 INTRODUCTION

1.1 Scientific Background

Idiopathic nephrotic syndrome in childhood

Clinical course and epidemiology

Idiopathic nephrotic syndrome in childhood, defined as the combination of heavy proteinuria (>40 mg/m² body surface area (BSA) per h) and hypalbuminemia (<25 g/L), accompanied by edema and hyperlipidemia, is a rare, relapsing disease with an incidence of 1.8 per 100.000 children below 16 years of age in Germany (ESPED registry 2005-2006), resulting in an annual rate of 200-250 patients [1]. The classification according to the four following categories is important for the clinical diagnostics, treatment and prognosis of the nephrotic syndrome in childhood: etiology, age at onset, histology, response to glucocorticoids. The primary idiopathic nephrotic syndrome with a typical onset of age (1-10 years of age) should be differentiated from patients with secondary causes or patients with age of onset younger than one year (congenital and infantile forms) or elder than 10 years of age. Approximately 80% of the children with idiopathic nephrotic syndrome have minimal change disease in renal biopsy, approximately 7% focal segmental glomerulosclerosis. The most important prognostic factor is steroid-sensitivity occurring in over 90% of the patients.

Treatment

The treatment of the first episode implies two aspects: (i) induction of remission, (ii) sustainment of remission. The German Society for Pediatric Nephrology (GPN), formerly known as Arbeitsgemeinschaft für pädiatrische Nephrologie (APN), formed the foundation for the standard of care of children with the nephrotic syndrome [2-7]. Thus, the recent guideline for the initial treatment of the first episode of a nephrotic syndrome recommends in detail: 60 mg prednisone/m² BSA per day for 6 weeks followed by alternate day prednisone 40 mg/m² BSA for another 6 weeks [8]. In case of steroid-sensitivity remission usually occurs within 7-14 days of treatment; the over-all duration of initial prednisone treatment is 12 weeks in order to sustain remission. This regimen has a relapse rate of 51% within 24 months after initial prednisone therapy, and a rate of frequent relapsers of 29% is expected.

Side effects of treatment

Even though being effective, this treatment is associated with pronounced glucocorticoid-associated toxicity due to high-dose prednisone administration over a prolonged period of time. The major side effects, which have been shown consistently in previous studies [3,4,9], comprise obesity, striae, hypertrichosis, cataract, glaucoma, arterial hypertension, psychological disturbances, growth failure, disturbances in carbohydrate and lipid metabolism, osteopenia, and avascular bone necrosis. Not all of these side effects are fully reversible after cessation of steroid therapy. In one study for example, excess weight gain during initial steroid therapy persisted in a significant subset (47%) of patients following cessation of glucocorticoid therapy [10]. Excess weight following cessation of glucocorticoid therapy was associated with hyperlipidemia, which might enhance the cardiovascular risk of these patients in the long-run [11]. Furthermore, a recent GPN study on the initial treatment of the nephrotic syndrome revealed no advantage of an intensified immunosuppressive protocol in terms of occurrence of relapses during a follow-up of 24 months [5]. Other studies have shown that higher exposure to glucocorticoids in the initial therapy leads to more toxicity without a substantial gain of efficacy, which is prevention of future relapses [8,12].

Treatment of relapses

Relapses of idiopathic nephrotic syndrome in childhood are generally treated with glucocorticoids according to a standard regimen 60 mg prednisone/m² BSA per day until the urine is free of protein for three consecutive days followed by alternate day prednisone 40 mg/m² BSA for 4 weeks. Depending on the number of relapses this aggravates the side effects. In case of frequent relapses a glucocorticoid-free therapy (cyclosporine, mycophenolate mofetil) for sustaining remission has to be considered.

Role of mycophenolate mofetil in the treatment of nephrotic syndrome in childhood

Mycophenolate mofetil (MMF), the pro-drug of its active moiety mycophenolic acid (MPA), is a potent, selective and reversible inhibitor of inosine monophosphate dehydrogenase (IMPDH), the key enzyme of de novo purine synthesis in activated lymphocytes. Mycophenolate mofetil is effective in sustaining remission in patients with frequently relapsing or glucocorticoiddependent nephrotic syndrome. Analysis via the PubMed search engine using the key words "nephrotic syndrome" "children" "mycophenolate mofetil" AND "clinical trials" revealed 12 studies, 6 of them prospective, including one phase II Bayesian trial [13-18]. Four prospective studies in patients with frequently relapsing or glucocorticoid-dependent nephrotic syndrome explored the possibility of withdrawing prednisone, which was successful in >50% of patients without further relapses [13,15-17]. In children with glucocorticoid-dependent nephrotic syndrome on MMF, Dorresteijn et al. reported of relapse rates of 25% after 6 months and 45% after 12 months, respectively [18]. In a phase II Bayesian trial, Baudouin et al. confirmed the effect of MMF in reducing relapse rates and glucocorticoid dose in children with glucocorticoiddependent nephrotic syndrome [14]. A recent GPN study on the maintenance of remission in children with frequently relapsing or steroid-dependent SDNS has shown that MMF in adequate exposure is as effective as cyclosporine (CsA) in sustaining remission without the burden of CsA-induced nephrotoxicity and neurotoxicity (ISRCTN61976169) [19]. Benz et al. have shown that the efficacy of MMF regarding the prevention of relapses in these patients can be optimized by achieving a MPA exposure (MPA-AUC₀₋₁₂) of >64 mg x h/L with a sensitivity of 100% and a specificity of 89% without any relevant toxicity [20].

So far, no studies with mycophenolate mofetil for the initial treatment of the steroid-sensitive nephrotic syndrome in children have been performed. However, it seems coherent to use the efficacy of MMF also for sustaining remission in the initial treatment of SSNS after achieved remission and to benefit from its lower toxicity compared to glucocorticoids.

1.2 Study Rationale/Justification

The initial treatment of the idiopathic nephrotic syndrome in children requires sufficient immunosuppressive therapy to induce and sustain remission, but should avoid toxicity, since the intensity of the initial treatment does not influence the long-term course of the disease. Our hypothesized novel treatment protocol has the potential to reduce the burden of glucocorticoid-associated side effects and associated cardiovascular risk factors, if the novel protocol is equally efficacious as the standard therapy. If our hypothesis turns out to be true, this novel therapy will become the standard of care for the initial treatment of steroid-sensitive nephrotic syndrome in children.

1.3 Risk-benefit Assessment

MMF is effective in sustaining remission in patients with the frequently relapsing steroidsensitive nephrotic syndrome [13,14,19]. Therefore, after achieved remission the risk for immediate relapse is low, even during the initial manifestation of SSNS. If the number of patients with relapses after intervention is higher than expected (experimental intervention is inferior to control group), prednisone will be given anyway for induction of remission; the over-all

prognosis will therefore not be influenced. On the other hand, the patients in the experimental group have the potential to benefit significantly because of less glucocorticoid-associated toxicity.

The most frequently observed side effects of mycophenolate mofetil are gastrointestinal symptoms such as nausea, vomiting, stomach pain and diarrhea, hematological symptoms such as leukopenia, anemia and rarely thrombocytopenia and an enhanced susceptibility for infections. In general, these side effects occur more frequently and have a higher clinical significance, when MMF is administered in conjunction with other immunosuppressive medications such as cyclosporine or tacrolimus, as indicated after solid organ transplantation. When MMF is administered as monotherapy, for example in patients with frequently relapsing steroid-sensitive nephrotic syndrome, the frequency and severity of these side effects are markedly lower [13-18] and these side effects will be systematically evaluated during the study visits.

In order to acknowledge recent reported adverse events (hypogammaglobulinemia and bronchiectasia) in patients after solid organ transplantation and treated with MMF together with other immunosuppressive co-medication in the long-time run, these adverse events are monitored closely in the INTENT study (see 5.4.7.), despite these events are very unlikely to happen due to the short administration period.

2 STUDY OBJECTIVES AND ENDPOINTS

2.1 Primary Objective and Primary Endpoint

The main purpose of the study is to show that MMF in the initial treatment of SSNS in children is not inferior regarding maintenance of initial remission and subsequent relapse rate compared to the standard high-dose prednisone regimen.

The primary efficacy endpoint is occurrence of treated relapse within 24 months after completion of initial treatment (rationale: this endpoint was chosen in all previous studies on the initial treatment of SSNS in children and is also the primary endpoint in various meta-analyses on this topic [3,4,5,7,8]).

Relapses of the SSNS will primarily be detected by daily urine dip stick analysis (Albustix[®], PZN 1266154), which is performed and documented by the patients and parents themselves. Definition of relapse: Relapse is denoted by a reappearance of proteinuria for 3 consecutive days:

Albustix[®]≥2+ (first or second morning urine) (for interpretation see Albustix[®])

or

urine protein/creatinine (Up/c) ratio ≥2 g/g (first or second morning urine)

or

urine protein level of ≥40mg/m² BSA/h (urine collection for minimum 12 hours)

Relapses with and without treatment are documented. The primary endpoint is fulfilled by the first treated relapse.

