3 STUDY DESIGN AND DESCRIPTION

3.1 Study design

This is a prospective, randomized, multicenter, controlled, open, parallel group phase III study.

After initiation of the study, patients will be screened consecutively and eligible patients will be enrolled into the study at each center. To achieve comparable intervention groups and to minimize a potential selection bias, patients will be allocated in a concealed fashion by means of randomization using a centralized web-based tool (www.randomizer.at).

Each sites' principal investigator has to declare to the coordinating investigator/sponsor that he/she will conduct the study according to the protocol, ethical rules, and to provide the support as needed. To minimize a potential performance bias, this will be fixed in a contract prior to commencing the study. The clinical monitor will introduce the sites in detail to study procedures and documentation in advance.

Bias by potential influential factors will be addressed by inclusion as covariates into the statistical analysis. Independent clinical on-site monitoring to ensure patients safety and integrity of the clinical data in adherence to study protocol will focus on source data documentation, correctness of data, and adherence to study procedures, e.g. randomization and treatment.

Based on the performed interventions and planned analysis blinding is not feasible to minimize a detection bias, because the interventions can easily be differentiated due to visible side effects such as obesity, which is only expected in the control group. Furthermore, MMF is used in liquid form and prednisone as a tablet. The primary endpoint is based on standardized diagnostic work-up results, i.e. is an objective criteria.

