	* If the results of Albustix™ are not clear, first or second morning urine or a specimen of a urine collection has to be checked. This can be performed at the study center or at any pediatrician. A spot urine sample with a protein/creatinine (Up/c) ratio of ≥ 2 g/g or a urine protein excretion of ≥ 40 mg/m² BSA/h (urine collection for a minimum of 12 hours) will define the relapse.	
	In case of a relapse the study center should be informed by the persons having care and custody of the child.	
	After diagnosis of a relapse, a time period of up to 10 days is allowed for a possible spontaneous remission, before standard therapy for relapse is initiated (see below). This decision is at the discretion of the study center. Treatment of the relapse has to be initiated according to the standard therapy of the GPN (see below).	
	Relapses with and without treatment are documented in the eCRF.	
Standard therapy for relapse of idiopathic nephrotic syndrome in children	Prednisone 60 mg/m ² BSA/d (maximum 80 mg) until remission (this dose is given in one dose or in two to three divided dosages per day with highest dosage in the morning), which is denoted by a reduction of urinary protein concentration or excretion in the first or second morning urine for 3 consecutive days to:	[4,8]
	Albustix [™] negative or trace or	
	$\frac{d}{Up/c} \le 0.2 \text{ g/g}^*$	
	or urine protein excretion of ≤ 4 mg/m² BSA/h (urine collection for a minimum of 12 hours)*	
	* If the results of Albustix™ are doubtful, first or second morning urine or a specimen of a urine collection has to be checked. This can be performed at the study center or at any pediatrician.	
	Followed by	
	Prednisone 40 mg/m ² BSA (maximum 60 mg) on alternate days for 4 weeks	

	(entire dosage is given in the morning)	
	(alternate day = every second day)	
Frequently relapsing nephrotic syndrome	Relapses occur 4 or more times in any 12 month period or 2 or more relapses within the first 6 months period after initial response.	[4,23,25]
Steroid-dependent nephrotic syndrome (SDNS)	Relapses occur during the alternate day prednisone treatment period or within 2 weeks after discontinuation of prednisone treatment.	[4,23,25]
Steroid-resistant nephrotic syndrome (SRNS)	No remission within 28 days after initiation of standard prednisone therapy for the first episode of idiopathic nephrotic syndrome in children	[4,23,25]
eGFR	Estimated glomerular filtration rate	[25,26]
	Formula = (K * height [cm])/serum creatinine [mg/dl]	

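### The open-label primary endpoint is called objective, yet it counts only treated relapses, with an unblinded choice to wait up to 10 days and relapse wording that is not uniform

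*Protocol*

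**What the plan says.** Protocol section 3.1 sets the design: "This is a prospective, randomized, multicenter, controlled, open, parallel group phase III study". After explaining why blinding is not feasible, it adds: "The primary endpoint is based on standardized diagnostic work-up results, i.e. is an objective criteria".

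Section 2.1 says that detection rests mainly on daily dipstick testing, "which is performed and documented by the patients and parents themselves". It then fixes what counts: "Relapses with and without treatment are documented. The primary endpoint is fulfilled by the first treated relapse".

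The Relapse entry of Appendix 1 says that after diagnosis "a time period of up to 10 days is allowed for a possible spontaneous remission, before standard therapy for relapse is initiated", and continues: "This decision is at the discretion of the study center". Section 6.1, under treatment of relapses, allows the same window and says that no guideline settles immediate against deferred treatment. Both places require that treatment, when given, follows the standard relapse therapy.

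The definition of relapse appears in several forms:

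- Section 2.1 and the head of the Appendix 1 entry: "Relapse is denoted by a reappearance of proteinuria for 3 consecutive days", placed ahead of all three criteria (dipstick, Up/c ratio, timed collection).
- The Appendix 1 footnote, for dipstick results that are not clear: "A spot urine sample with a protein/creatinine (Up/c) ratio of" at least 2 g/g, or a timed collection of at least 40 mg/m² BSA/h, defines the relapse. No 3-day condition is repeated.
- The visit descriptions in section 6.1 (visits 2 to 8): the 3 days are attached to the dipstick only, and a 2+ result is glossed as above 30 mg/dL. The dipstick table in the same section and Appendix 2 put 30 mg/dL at 1+ and 100 mg/dL at 2+.

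**The concern.** An endpoint that needs a decision to start treatment is not determined by the diagnostic result alone. Here that decision includes a permitted wait, and the person deciding knows whether the child received MMF or prednisone. If centers were readier to wait in one arm than in the other, the counted event rates would differ between arms with no difference in disease. In a non-inferiority trial this can work either way. Fewer counted events on MMF pull the result towards non-inferiority, and fewer counted events on prednisone cost power. The confirmatory analyses in the ITT and PP populations give no protection against each other, because both count treated relapses only.

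The uneven definition adds a second source of judgment: whether one spot urine or collection is enough, or three days are needed, and which dipstick value the 2+ gloss stands for.

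**Working it through.** **1. The stated design reproduces.** Inputs from section 8.1: 51% in both arms, margin 0.15, one-sided 5%, power 80%. The Farrington-Manning restricted estimates are 0.5846 and 0.4346.

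- s0 = √(0.5846×0.4154 + 0.4346×0.5654) = 0.699; s1 = √(2×0.51×0.49) = 0.707.
- n per arm = [(1.645×0.699 + 0.842×0.707)/0.15]² = 135.3, so 136 per arm and 272 in total, as stated.
- 272/0.80 = 340, as stated.
- Exact enumeration of the test at 136 per arm: power 80.1%; probability of declaring non-inferiority at 66% vs 51% is 5.4%.

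The sample size is not in question.

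**2. Ceiling on the shift.** The documents give no share of relapses left untreated, so a 90% vs 80% split is assumed. With one relapse per child and the same relapse risk p in both arms, the counted rates are 0.90p and 0.80p and the shift is 0.10p.

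- p = 0.51: 5.1 points; 5.1/15 = 34% of the margin.
- p = 0.66 (51% plus the margin): 6.6 points; 6.6/15 = 44%.

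**3. Allowing for later relapses.** The endpoint is the first treated relapse at any time in the 24 months, so a child whose first relapse remits untreated can still be counted later. Section 1.1 expects 29% frequent relapsers, and by Appendix 1 these have at least two relapses. Assume exactly two, with independent treatment decisions, and one relapse in every other relapsing child. A two-relapse child is missed with probability 0.10² = 1% vs 0.20² = 4%, a gap of 3 points instead of 10.

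- p = 0.51, 29% read as a share of all children: 0.29×3 + 0.22×10 = 3.1 points (20% of the margin).
- p = 0.51, 29% read as a share of relapsers: 0.51×(0.29×3 + 0.71×10) = 4.1 points (27%).
- p = 0.66, scaling both by 66/51: 4.0 and 5.3 points (26% and 35%).

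More relapses per child shrink the shift further. Strong correlation of decisions within a child moves it back towards the ceiling.

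**4. Effect on the decision.** Let f be the share of relapsing children in one arm who are never counted, over and above the other arm (an assumption). Exact enumeration at 136 per arm gives:

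| f | True 66% vs 51%, f in MMF arm: difference seen | Probability of declaring non-inferiority | True 51% vs 51%, f in prednisone arm: power |
|---|---|---|---|
| 0 | 15.0 points | 5.4% | 80.1% |
| 2% | 13.7 | 8.4% | 75.0% |
| 5% | 11.7 | 14.8% | 66.4% |
| 10% | 8.4 | 30.9% | 50.4% |

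The 10% row is the ceiling case: 0.66×0.90 − 0.51 = 0.084, a loss of 6.6 points.

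**5. Equal non-treatment.** If the same 10% go uncounted in both arms, a true 15-point difference shrinks to 0.90×15 = 13.5 points, and the probability of declaring non-inferiority rises from 5.4% to 8.5%. This dilution adds to any imbalance: with true rates of 66% and 51% and shares treated of 80% and 90%, 0.528 − 0.459 = 6.9 points, a loss of 8.1, of which 1.5 is dilution and 6.6 imbalance.

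**The case against.** Much can be said for the plan, and part of it stands.

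- A reader might infer that section 3.1 gives up blinding because the endpoint is objective. It does not. Its reasons are visible side effects and different formulations; objectivity is an added reassurance.
- A reader might infer that centers are free to leave relapses untreated. The text is narrower: treatment has to follow the standard therapy, and only a wait of up to 10 days is open. A relapse that persists is treated and counts.
- A reader might see two flatly contradictory definitions. The Appendix 1 footnote applies only to unclear dipsticks and can be read as confirmation after several days of proteinuria. The numeric Up/c and excretion thresholds agree throughout. What remains is ambiguity about the 3-day condition and the mg/dL gloss, and it is common to both arms.
- The endpoint has a stated precedent in earlier trials and meta-analyses. Untreated relapses are documented, and secondary endpoints 1a to 1d in section 2.2 are not limited to treated relapses. Further sensitivity analyses are ordinary content of a statistical analysis plan, so their absence from the protocol is not in itself an error.

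What this leaves is the protocol's own text. Precedent does not make an unblinded treatment decision objective. The secondary relapse endpoints are evaluated descriptively under section 8.4, with no test against 0.15. The sensitivity analyses named there vary covariates, populations and drop-out values, but not the event.

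**Conclusion.** The concern holds in limited form. The statement in section 3.1 is incomplete: the diagnostic thresholds are numeric, but the primary event also depends on a treatment decision by staff who know the arm. The relapse passages need reconciling.

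The exposure is confined to relapses that would remit within the 10-day window. For an assumed 10-point difference between arms in the share treated, the resulting shift is at most about 5.1 points at 51% risk and 6.6 points at 66% (34-44% of the margin). It is about 3 to 5 points if frequent relapsers have a second, independent chance to be counted. The split is an assumption; the documents neither support nor exclude it.

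It would be tempting to conclude that the trial is biased towards MMF. The documents do not support that: nothing in them says in which arm centers would wait longer, and waiting longer in the prednisone arm would reduce power instead. The sample size stands.

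**What to change.** - Pre-specify, as a supportive sensitivity analysis, the same Farrington-Manning test (margin 0.15, ITT and PP) on first documented relapse in the same 24-month period, treated or not. It should not be required to agree with the primary result: that would make it co-primary in effect, with a power cost that the design does not provide for.
- Tabulate by arm the share of relapses treated and the days from relapse to start of treatment.
- Reconcile section 2.1, the Appendix 1 entry and its footnote, the visit text and the 2+ gloss into one definition. Which wording is right is for the investigators.
- Qualify section 3.1 to say that the diagnostic thresholds are objective but the event also depends on an unblinded treatment decision.

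The cost is one further run of a planned test, a table and text changes, plus a possible discordant result to explain. Date of relapse, criterion met and treatment given are already recorded. The protocol mentions the relapse medication but not explicitly its start date, so the eCRF should be checked for that item. How relapses are treated does not change, and neither does the sample size, because the primary endpoint and its test stay as they are. The supportive test has the planned power only if the 51% rate also holds for all relapses, treated or not.
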